7.2. Rationale and Discussion of Study Design

The first part of this study is a randomized, double-blind, placebo-controlled study of the safety, tolerability, PK, and efficacy study of trifarotene cream HE1 100 µg/g and 200 µg/g in adults and adolescents with LI.

In a previous proof-of-concept study (RD.03.SRE.40181E), subjects with LI applied trifarotene 50 and 100 µg/g cream to limited areas and results demonstrated a decrease in scaling with good safety and tolerance. In a phase 1 study in healthy Japanese and non-Japanese subjects (RD.03.SPR.103813), repeated topical applications of trifarotene (CD5789 cream HE1) 100 µg/g and 200 µg/g resulted in low and similar CD5789 systemic levels in all the cohorts. These studies are fully described in the current Investigational Brochure.

To ensure safety, this phase 2 study will begin with an initial cohort (Cohort A) of 15 adults randomized 1:1:1 to trifarotene cream HE1 100 µg/g, 200 µg/g, or vehicle to be applied twice weekly. An independent DSMB will review aggregate safety and tolerability data from the initial 15 subjects' first 28 days of treatment. If no safety issues are identified, 105 adults and adolescents (ages 12–17 years, inclusive) will be allowed to enroll in Cohort B and randomized to trifarotene cream HE1 100 µg/g, trifarotene cream HE1 200 µg/g, or vehicle and treated twice weekly in the same manner as subjects in Cohort A. All subjects in the randomized, double-blind portion of the study will be treated for up to 12 weeks and data on safety, tolerability, PK, and efficacy collected.

Adult and adolescent subjects who successfully complete the initial 12 weeks of double-blind treatment will have the option to enter an OLE with trifarotene cream HE1 200 µg/g twice weekly for up to 12 weeks.

The OLE will collect additional safety, tolerability, PK, and efficacy data. As designed, this study will provide important information on safety, tolerability, and PK with dosing of adolescents and adults with LI for up to 6 months.

The protocol includes appropriate monitoring for safety and tolerability. If subjects develop significant local application site reactions or tolerability issues, the protocol includes language for reducing the frequency of application or halting study drug application until the symptoms abate.

7.3. Selection of Doses in the Study

Based on the results from Study RD.03.SRE.40181E and Study SRE.103813, the doses of 100 µg/g and 200 µg/g were selected for further investigation in adult and adolescent subjects with moderate to severe LI to determine which of the 2 doses is most effective.. The PoC study demonstrated efficacious treatment with 100 µg/g in adults. The PK and tolerability study showed that, when the frequency of application was reduced from daily to twice weekly, the 200 µg/g cream HE1 had good local tolerability.

Therefore, the current study will use these doses compared with vehicle, applied twice weekly on up to approximately 90% BSA in subjects with LI. The OLE will evaluate the long-term safety of the higher dose in this patient population.

7.4. Study Sites

The study will take place at approximately 40 sites in North America, Europe, Israel, and Australia.

7.5. Point of Contact

A point of contact will be identified to provide information to subjects about where to obtain information on the study, the rights of subjects, and whom to contact in case of a study-related injury. This information will be provided in the subject information and informed consent form (ICF).

7.6. End of Study Definition

A clinical trial is considered completed when the last participant's last study visit has occurred.

8. SUBJECT POPULATION

8.1. Selection of Study Population and Diagnosis

Diagnosis of LI for the purposes of this study will be a clinical diagnosis. Although some younger subjects may have had genetic testing, older subjects may not.

While LI is a rare disease and subject enrollment may be challenging, due to possible bias introduced by including household members in the same study, it is recommended that only 1 household member be included in the study to maintain the blind and ensure all assessments are independent.

8.2. Study Entry Criteria

8.2.1 Inclusion Criteria

A subject will be eligible for study participation if he or she meets all of the following criteria:

1. For Cohort A: subject is ≥ 18 years old; for Cohort B: subject is ≥ 12 years old.
2. Subject has known diagnosis of LI.
3. Subject has moderate to severe (IGA 3–4) LI on the IGA of LI severity.
4. Subject has signed an ICF at Screening before any investigational procedures. Subjects < 18 years of age (or Age of Majority) must sign an assent form in conjunction with an ICF signed by the parent/legal representative.
5. Subject who is participating in optional photography has signed a photography ICF.
6. Subject who is participating in the optional PK substudy has signed a PK ICF.
7. Subject is not of childbearing potential, i.e., a female who has not yet begun menstruating or who is postmenopausal (absence of menstrual bleeding for 1 year before Baseline, without any other medical reason, hysterectomy or bilateral oophorectomy),
OR
 - Subject is a woman of childbearing potential (WOCBP) or a male subject with sexual partners capable of reproduction who agrees to use 2 effective forms of contraception during the study and for at least 1 month after the last study drug application. The 2 authorized forms of contraception are condom used with 1 of the following methods of contraception:
 - bilateral tubal ligation
 - combined oral contraceptives (estrogens and progesterone) or implanted or injectable contraceptives with a stable dose for at least 1 month before Baseline; hormonal contraceptives must inhibit ovulation
 - hormonal intrauterine device (IUD) inserted at least 1 month before Baseline

OR

Agrees to abstain from heterosexual intercourse during study participation and for 1 month after the last application of study drug and to use a highly effective contraceptive as backup if he or she becomes sexually active during the study. Abstinence is only acceptable if this is the subject's usual lifestyle. Periodic abstinence (calendar, symptothermal, postovulation methods), withdrawal (coitus interruptus), spermicides only, and lactational amenorrhoea method are not acceptable methods of contraception.

AND

Male subjects may not donate sperm during the study and for at least 1 month after the last study drug application.

Note: Subjects who are premenstrual at Screening but begin menses during the study should follow the pregnancy testing schedule for WOCBP and must abstain from sexual intercourse while in the study and for at least 1 month after the last study drug application.

8. Women of child-bearing potential must be nonlactating and have negative pregnancy test results at Screening (serum) and on Day 1 before study drug administration (urine).
9. Subject is reliable and capable of adhering to the protocol and visit schedule, in the investigator's judgment, and has signed informed consent/assent, as applicable.
10. Subject is taking no more than 3500 IU/day Vitamin A (e.g., as in a multivitamin).

8.2.2 Exclusion Criteria

A subject will be excluded from the study if he or she meets any of the following criteria:

1. Subject has any variant of ichthyosis other than LI or another disorder of keratinization, including syndromic ichthyoses.
2. Subject has current moderate or severe stinging/burning at Screening.
3. Subject has an ongoing cutaneous infection or any other significant concomitant skin disease (other than the LI) which, in the investigator's opinion, may interfere with the study assessments.
4. Subject with a known lipid disorder (hypertriglyceridemia >200 mg/dL, hypercholesterolemia >250 mg/dL) unless well controlled by stable doses of lipid-lowering agents for at least 6 months.
5. Subject was previously treated with trifarotene/CD5789 in an acne or ichthyosis study.
6. Subject has any other significant concomitant disease, or poorly controlled medical condition other than LI that in the investigator's opinion may put him or her at risk if he or she takes part in the study, and/or that may interfere with the study assessments.
7. Subject has a medical condition that potentially alters bone metabolism (e.g., osteoporosis, thyroid dysfunction, Cushing syndrome, Crohn's disease, or ulcerative colitis).
8. Subject is being treated for major depression disorder and/or has a history of major depression or suicide attempt requiring hospitalization, medications, and close psychiatric surveillance to prevent suicide attempts.
9. Subject with positive serology for hepatitis B surface antigen, hepatitis C, or are known to be HIV positive or to have AIDS at Screening.
10. Subject with any of the following laboratory values at Screening:
 - a. Aspartate aminotransferase or alanine aminotransferase $>1.5 \times$ upper limit of normal defined by the laboratory
 - b. Total bilirubin >1.1 mg/dL or, in case of Gilbert's syndrome, total bilirubin >3 mg/dL
 - c. Hemoglobin <12.5 g/dL for men and <11.5 g/dL for women
 - d. Platelets $<150 \times 10^9/L$ or $>400 \times 10^9/L$.

11. Subject has any clinically other significant abnormal laboratory value (hematology, chemistry, or urinalysis) at Screening that, in the investigator's opinion, may put the subject at risk if he or she takes part in the study, and/or that may interfere with the study assessments.
12. Subject has had recent systemic malignancy (e.g., within 5 years) with exception of nonmelanoma skin cancer or cervical intraepithelial neoplasia of Grade 1 who are >6 months post-treatment.
13. Subject has a history of long QT syndrome or clinically significant ECG abnormalities, including clinically significant conduction disorders or significant arrhythmias, QTcF interval >450 ms, PR interval is not between 120 and 220 ms (inclusive), HR >100 bpm or <50 bpm, QRS interval >110 ms, or QT intervals that cannot be consistently analyzed.
14. Subject has a known allergy or sensitivity to any of the components of the investigational products.
15. Subject has been exposed to excessive UV radiations on the treated zones within 1 month before Baseline visit or is planning intensive UV exposure during the study (e.g., occupational exposure to the sun, sunbathing, phototherapy, etc.).
16. Subject is inherently sensitive to sunlight.
17. Subject is unable or unwilling to stop use of topical or systemic retinoids.
18. Subject is presumed to be abusing drug or alcohol at Screening or Baseline Visits based on medical history or current clinical symptoms.
19. Subject is participating in another interventional clinical trial.
20. Subject is institutionalized.
21. Subject is in any way related to the sponsor, investigator, or site personnel.

8.3. Premature Subject Withdrawal

All subjects will be advised that they are free to withdraw from participation in this study at any time, for any reason, and without prejudice. The investigator should make every reasonable attempt to keep subjects in the study; however, subjects must be withdrawn from the study if they withdraw consent to participate. Investigators must attempt to contact subjects who fail to attend scheduled visits by telephone or other means to exclude the possibility of an AE being the cause of withdrawal. Should this be the cause, the AE must be documented, reported, and followed as described in Section 11.2.

The sponsor reserves the right to request the withdrawal of a subject due to protocol deviations or other reasons.

The investigator also has the right to withdraw subjects from the study at any time for lack of therapeutic effect that is intolerable or otherwise unacceptable to the subject, for intolerable or unacceptable AEs, intercurrent illness, noncompliance with study procedures, administrative reasons, or in the investigator's opinion, to protect the subject's best interest.

If a subject is withdrawn before completing the study, the reason for withdrawal and the date of discontinuation will be recorded on the appropriate page of the electronic case report form (eCRF). Whenever possible and reasonable, the evaluations that were to be conducted at the completion of the study should be performed at the time of premature discontinuation.

8.4. Discontinuation of Study Intervention

Discontinuation from study treatment does not mean withdrawal from the study, and the remaining study procedures should be completed as indicated in the study protocol (see Section 10.2.4.5). If a clinically significant finding is identified (including, but not limited to changes from Baseline) after enrollment, the investigator or qualified designee will determine if any change in participant management is needed. Any new clinically relevant finding will be reported as an AE.

An investigator must discontinue a participant's study treatment for any of the following reasons:

- Pregnancy
- Significant study intervention noncompliance
- If any clinical AE, laboratory abnormality, or other medical condition or situation occurs such that continued participation in the study would result in a significant burden to the participant
- If the participant meets an exclusion criterion (either newly developed or not previously recognized) that precludes further study participation

The reason for discontinuation of study treatment will be recorded on the eCRF. Subjects who sign the informed consent form and are randomized but do not receive the study intervention may be replaced. Subjects who sign the informed consent form, are randomized, and receive the study intervention, and subsequently discontinue study treatment, or are withdrawn from the study will not be replaced.

A participant will be considered lost to follow-up if he or she fails to return for 3 scheduled visits and is unable to be contacted by the study site staff.

The following actions must be taken if a participant fails to return to the clinic for a required study visit:

- The site will attempt to contact the participant and reschedule the missed visit and counsel the participant on the importance of maintaining the assigned visit schedule and ascertain if the participant wishes to and/or should continue in the study.
- Before a participant is deemed lost to follow-up, the investigator or designee will make every effort to regain contact with the participant (where possible, 3 telephone calls and, if necessary, a certified letter to the participant's last known mailing address or local equivalent methods). These contact attempts should be documented in the participant's medical record or study file.
- Should the participant continue to be unreachable, he or she will be considered to have withdrawn from the study with a primary reason of lost to follow-up.

8.5. Subject Replacement Criteria

Withdrawn subjects will not be replaced. If a substantial number of subjects are withdrawn from the study, the sponsor will evaluate the need for developing replacement criteria.

Randomized subjects withdrawn from the study may not reenter. The subject number for a withdrawn subject will not be reassigned to another subject.

9. TREATMENTS

9.1. Identification of Investigational Product(s)

Trifarotene cream HE1 is a cream containing 100 or 200 µg/g (0.01% [w/w] or 0.02% [w/w], respectively) of CD5789 and the following excipients: purified water, propylene glycol, allantoin, glycerin, medium-chain triglycerides, polypropylene glycol 15 stearyl ether, cyclomethicone, phenoxyethanol, copolymer of acrylamide and sodium acryloyldimethyltaurate, dispersion 40% in isohexadecane (simulgel 600 PHA), sodium benzoate, butylated hydroxytoluene, and gluconolactone. It is a potent RAR γ agonist characterized by its high specificity to this receptor.

Vehicle contains the same ingredients, without the CD5789.

Trifarotene cream HE1 and vehicle will be provided in cream form for topical application and will be supplied in 50-g tubes from which a maximum of 36 g of IP may be extracted,

Trifarotene cream HE1 and vehicle will be supplied by G. Production, Inc. (Galderma) in Baie-D'Urfé, QC, Canada.

9.2. Treatments Administered

For the Double-blind Treatment Period, a fixed dose (determined at Visit 2) of trifarotene cream HE1 100 µg/g or 200 µg/g or vehicle cream will be applied topically twice weekly on up to 90% BSA of each subject. The IP should be applied thinly and gently rubbed in.

Study staff will apply the first administration of IP in the clinic on Day 1 after Baseline measurements, and the amount of IP used will be measured (i.e., 50-g tube will be measured before and after application to determine amount used). If the product will be applied at home by someone other than the study subject, it is recommended that person assist with application at the first visit to learn how the IP is applied.

The maximum dose per application is 36 g (i.e., 1 tube). Subjects will receive an adequate number of tubes to use 1 tube per application and will use a new tube for each treatment day. Subjects may use less than full amount of product in a tube. Subjects will continue treatment for up to 12 weeks.

After the Day 1 visit, subjects will apply approximately the same amount (up to 36 g) of study drug as for the first dose on up to 90% of BSA twice weekly, sparing the scalp, inguinal, and axillary areas. Subjects with heavy facial hair should not apply IP to hair-bearing areas. Persons other than the study subject applying the study drug must wash their hands after application or use disposable vinyl gloves. In addition, a long-handled applicator will be provided for application on the back. The applicator must be washed with warm water and soap after every application.

Trifarotene cream should not come into contact with the eyes, mouth, angles of the nose, or mucous membranes. For the ectropion treatment, Q-tips are recommended for precise application on eyelids, without contact to the eye or conjunctiva. If the IP gets into the eye, it must be flushed immediately with warm water. In case of eye irritation, the subject must be seen by an ophthalmologist.

For the OLE, all subjects will receive trifarotene cream HE1 200 µg/g and apply the same fixed dose in the same manner as in the Double-blind Period for an additional 12 weeks.

Visits for PK must occur at least 24 hours after the last application of the IP to avoid contamination of the blood samples with any IP that may have remained in the skin after the last application.

Subjects should not apply IP on visit days until after the visit, unless they are participating in the PK substudy, in which case the IP will be applied in the clinic on Day 30 after the blood draw. Among subjects participating in the PK substudy, ensure the PK line is inserted before study drug application to prevent contamination with the IP and to protect the skin around the needle insertion point from study drug application.

9.3. Selection of Timing of Dose for Each Subject

Subjects will be randomized in a 1:1:1 ratio to trifarotene cream HE1 100 µg/g or 200 µg/g or vehicle cream. After Day 1, on which the study staff will apply the first administration of IP in the clinic, each subject will apply approximately the same amount of IP on up to 90% of their BSA twice weekly. It is suggested that each subject choose 2 specific days per week at least 3 days apart on which to apply their IP (e.g., Tuesday and Friday), and maintain that regimen throughout the study. Visits for PK must occur at least 24 hours after the last application of the IP to avoid contamination of the blood samples with any IP that may have remained on the skin after the last application. Subjects should not apply the IP on visit days until after the visit, unless they participate in the PK substudy, in which case the IP will be applied in the clinic on Day 30 after the PK blood draw.

All subjects will be provided with diaries in which to record study drug application (days/times) and any areas of skin not treated (e.g., due to local reactions).

If a subject misses an IP application, they should apply the IP as soon as they remember and record the date/time in the subject diary, then wait at least 3 days and continue their regimen.

Subjects should not shower, bathe, or swim for at least 4 hours after IP application. No occlusive dressings should be used on areas to which IP is applied.

Subjects who continue into the Open-label Extension will receive trifarotene cream HE1 200 µg/g and apply the same fixed dose in the same manner as in the Double-blind Period for an additional 12 weeks.

9.4. Dose Adjustment Criteria

Local tolerance will be followed very carefully during the study. Subjects will receive information on study drug use and stopping rules and will be instructed to contact the site with any safety/tolerability issues. Study personnel will telephone subjects in between scheduled visits (i.e., at Day 7 and Day 45) to assess safety; an unscheduled clinic visit may be performed, if necessary. During all clinic visits, the investigator will assess local tolerability on a 0-3 scale (0 = none, 1 = mild, 2 = moderate, 3 = severe) for each treated body area (chest/abdomen, back, arms, legs, and face/neck), and the following procedures will be followed:

- If a score of 2 (moderate) is recorded on a local tolerability assessment scale (stinging/burning, pruritus, erythema) on any treated area (e.g., the face), the study drug will be applied on this area only once weekly, until the score returns to <2. Continue to treat all other areas twice weekly provided the score is <2 on those areas.
- If a score of 3 (severe) is recorded on a local tolerability assessment scale (stinging/burning, pruritus, erythema) on any treated area, the study drug will not be applied on that area until the score is back to <3 (i.e., “drug holiday”). Continue to treat all other areas twice weekly provided the score is <2 on those areas.

Any changes in dosing must be documented in the subject diary and the eCRF.

9.4.1 Stopping Rules

A subject's treatment in either the Double-blind Period or the Open-label Extension must be stopped if any of the following occur:

- Subject becomes pregnant or suspects they are pregnant
- Subject has severe (score of 3) local application site AEs that do not abate with “drug holiday” and reintroduction of IP.
- Subject has clinically significant changes in laboratory values (liver function tests, cholesterol/triglycerides – which may occur with systemic retinoid use)

Any changes in dosing must be documented in the subject diary and the eCRF.

9.5. Treatment Compliance

Subjects will be asked to record their twice-weekly applications of IP in the diary during both the Double-blind Period and the OLE. Deviations from the planned doses (missed dose or timing) will be recorded on the subject's eCRF. Study personnel will review diaries at each visit and diaries will be collected as source documents. Information from subject diaries will be transcribed on the appropriate eCRF pages for documentation of subject compliance with the IP.

Study personnel will assess treatment compliance with IP regimens by weighing IP tubes before dispensing and upon return and by questioning the subject, at every postrandomization visit. A participant is compliant with study product if he or she takes at least 80% of the scheduled doses as assessed by diary entries, supplemented by tube weight. A subject who is not compliant (used 80–120% of IP tubes) will be counseled at each visit on the importance of using the IP as instructed.

Subjects who taper to once-weekly application or who take a “drug holiday” for tolerability will not be reported as having deviated from the protocol (see Section 9.4 for dose adjustment and stopping rules); any changes in dosing must be documented in the subject diary and the eCRF.

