9.11. Drug Accountability

The investigator must maintain adequate records showing the receipt, dispensing, return, or other disposition of the IPs, including the date, quantity, batch or code number, and identification of subjects (subject number) who received the IP. The investigator will not supply the IP to any person except those named as subinvestigators on the Form Food and Drug Administration (FDA) 1572, designated study personnel, and subjects in this study. The investigator will not dispense the IP from any study sites other than those listed on the Form FDA 1572. Investigational product(s) may not be relabeled or reassigned for use by other subjects. If any of the IP is not dispensed, is lost, stolen, spilled, unusable, or is received in a damaged container, this information must be documented and reported to the sponsor and appropriate regulatory agencies, as required.

Each subject will be given enough tubes of study drug to apply up to 1 tube-full (approximately 36 g of clinical trial material) per treatment day until the next study visit. Tubes will be packed 2 to a carton, and each subject will receive enough cartons to have the maximum number of tubes needed until the next study visit. The number of study drug tubes the subject needs to provide enough IP until the next visit is shown in [Table 9-2](#).

Table 9-2: Amount of Study Drug Needed Per Visit

Treatment Period	Number of Cartons	Number of Tubes
Double-blind Treatment Period		
Baseline	3	6
Day 14	4	8
Day 30	6	12
Day 60	6	12
OLE		
Day 90	3	6
Day 104	4	8
Day 120	6	12
Day 150	6	12

Each carton will be weighed before dispensing and subjects are to bring all cartons and tubes back at each study visit, whereupon study staff will weigh them again to estimate study drug use and compliance.

Upon completion of the study, the IP (partly used, unused, and empty tubes) must be left in the original packaging and returned to the sponsor or designee for destruction.

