13.1.1 Analysis Populations

The following 5 analysis populations are planned for the Double-blind Period of this study:

- Safety: all subjects who are randomized to treatment and receive at least 1 application of study drug in the Double-blind Period. This population will be the primary population for analyses of safety.
- Intent-to-treat (ITT): all randomized subjects. This population will be used as the primary population for the analysis of efficacy for the Double-blind Period of the study.
- Modified intent-to-treat (mITT): all subjects in the safety population with at least 1 postbaseline assessment of efficacy in the Double-blind Period.
- Per-protocol (PP): subjects in the mITT Population who met all inclusion criteria and no exclusion criteria, were compliant with study drug application, and who had no significant protocol deviations.
- Pharmacokinetic: all subjects in the Safety Population who have at least 1 plasma sample with quantifiable concentration. This population will be used to summarize all PK endpoints.

The following analysis populations are planned for the OLE of this study:

- OLE Safety: all subjects who complete the 12-week Double-blind Treatment Period and receive at least 1 application of study drug in the OLE.
- OLE ITT: all subjects who complete the 12-week Double-blind Treatment Period and sign the OLE informed consent.
- OLE mITT: all subjects in the OLE safety population with at least 1 assessment of efficacy after Visit 6.

- OLE PP: all subjects in the OLE mITT population who met all inclusion criteria and no exclusion criteria, were compliant with study drug application from baseline through EOT, and who had no significant protocol deviations throughout the study.

Inclusion in the analysis populations will be determined prior to database lock.

If a subject is randomized incorrectly or is administered the incorrect IP, analyses of the ITT and mITT populations will be based on the assigned treatment whereas all other analyses will be based on the actual treatment received.

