13.1.3 Exposure and Compliance

Investigational product administration will be summarized in terms of each subject's dose, and in terms of duration of exposure for each period. Descriptive statistics for these quantities, including the mean, median, SD, minimum, maximum, and quartiles, will be provided by treatment group. Additionally, the number of subjects who are compliant with investigational product will be presented by treatment group for the Double-blind Period and overall for the OLE.

Subjects who taper to once-weekly application or who take a "drug holiday" will not be reported as having deviated from the protocol.

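### Section 9.5 contradicts itself on compliance: one sentence sets a floor of 80% of doses with no cap, the next calls use of 80–120% of tubes not compliant, and correcting the likely slip still leaves overuse unsettled

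*Protocol*

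**What the plan says.** Protocol 9.5 (Treatment Compliance) has two adjacent sentences that bear on who is compliant.

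- The definition: "A participant is compliant with study product if he or she takes at least 80% of the scheduled doses as assessed by diary entries". The weight of the tubes serves as a supporting check. The rule has a floor and no ceiling.
- The counselling instruction: "A subject who is not compliant (used 80–120% of IP tubes) will be counseled at each visit". Here a range of tube use is attached to the subject who is *not* compliant, and the base of the percentage is not given.

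Other sections rely on the term:

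- 13.1.1 defines the PP set as "subjects in the mITT Population who met all inclusion criteria and no exclusion criteria, were compliant with study drug application" and without significant protocol deviations. The OLE PP set asks for compliance from baseline to end of treatment. Neither definition cites 9.5.
- 13.1.3 says that "the number of subjects who are compliant with investigational product will be presented by treatment group for the Double-blind Period".

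Two supply rules matter for the check. Under 9.2, subjects "use 1 tube per application and will use a new tube for each treatment day". Under 9.11, "each subject will receive enough cartons to have the maximum number of tubes needed until the next study visit", with the counts in Table 9-2.

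**The concern.** The range 80–120% is what one would expect to describe a compliant subject, yet it stands beside the words for a non-compliant one. Followed as printed, sites would counsel subjects who dose as planned, while those who use too little or too much would fall outside the parenthesis.

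Assuming a dropped word does not close the matter. The definition has no cap and the parenthesis has one, so someone still has to decide whether overuse is non-compliance. That question has substance here. Section 5.2 reports that daily use of this cream in healthy volunteers irritated the skin enough to force a cut to twice-weekly application.

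At stake are the counselling instruction, the compliance counts by treatment group, and who is in the PP and OLE PP sets. Section 8.4 also makes significant noncompliance a mandatory reason to stop treatment without defining it; whether 9.5 is meant to govern that is not stated.

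**Working it through.** The protocol gives no compliance count to reproduce, so the check applies both sentences to the planned and dispensed numbers.

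**Inputs**

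- Planned applications, Double-blind Period: twice weekly for 12 weeks (10.1.1), 2 × 12 = 24. If dosing runs to Day 90, 2 × 90/7 = 25.7, about 26.
- Tubes dispensed, Double-blind Period (Table 9-2): 6 + 8 + 12 + 12 = 38.
- One new tube per application (9.2), so tubes used and applications made are the same count.

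**Limits**

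- Of 24 planned: 0.8 × 24 = 19.2 and 1.2 × 24 = 28.8, so 20 to 28 applications lie within 80–120%.
- Of 26 planned: 0.8 × 26 = 20.8 and 1.2 × 26 = 31.2, so 21 to 31 lie within.
- Of 38 dispensed: 0.8 × 38 = 30.4 and 1.2 × 38 = 45.6, so 31 to 38 lie within (38 is the supply).
- Full use against dispensed tubes: 24/38 = 63% and 26/38 = 68%, both below 80%.

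**Where a subject is compliant by the definition and not compliant by the counselling sentence**

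| Reading of the parenthesis | Base | 24 planned | 26 planned |
|---|---|---|---|
| As printed (80–120% is not compliant) | planned | 20–28 | 21–31 |
| Outside 80–120% is not compliant | planned | 29–38 | 32–38 |
| As printed | dispensed | 31–38 | 31–38 |
| Outside 80–120% is not compliant | dispensed | 20–30 | 21–30 |

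Every reading leaves a conflict. In the first row the subjects in conflict include those who dose exactly as planned. The second row is the most likely intention, and there the sentences agree up to 120% of plan and part only on overuse. In percentages that row is 29/24 = 121% to 38/24 = 158%, or 32/26 = 123% to 38/26 = 146%. The fourth row shows why the base must be stated: measured against tubes dispensed, perfect adherence would count as non-compliant.

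Under the printed wording there is also a gap at the low end. On either base, a subject at 70% of plan is not compliant by the definition but is not described by the parenthesis.

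**The case against.** The strongest reply is that 9.5 has only one definition, the 80% floor, and that the next sentence is a counselling instruction with a word missing. No site would counsel a subject at 100% of plan, so the literal contradiction would do little harm in practice. This largely stands: a reader might infer that sites will really counsel adherent subjects, and nothing in the protocol makes that likely. It does not settle use above 120% or the base of the percentage.

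A reader might also infer that an overuser stays in or leaves the PP set purely according to which sentence is applied. The documents do not support that. Section 13.1.1 does not cite 9.5, and it separately excludes significant protocol deviators, so a subject 5 to 14 applications above 24 (29 − 24 to 38 − 24) might leave in any case. Membership is decided before database lock, and a statistical analysis plan may set the threshold. Such a plan could not, however, correct an instruction already given to sites.

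Finally, 38 tubes is a supply figure, not evidence of overuse. It is consistent with cover for visit windows: from Day 9 to Day 37 is 28 days, and 28 × 2/7 = 8 tubes, the number dispensed at Day 14. Tubes are returned and weighed at each visit, and 9.3 suggests treatment days at least 3 days apart. This stands. Use well above 120% is possible, but the documents give no rate for it.

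**Conclusion.** The point holds as a wording error that matters. Section 9.5 states a threshold wrongly, and the obvious correction leaves two sentences that disagree above 120% of plan and a percentage without a base. It should be corrected, but it is not a threat to the trial's main result: 13.1.4 bases the primary efficacy analysis on the intent-to-treat population, and the PP set serves only selected repeat analyses.

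The reach is limited to site counselling, the compliance table, and PP and OLE PP membership to the extent that these follow 9.5. The number of subjects affected cannot be derived from the documents and is probably small.

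The conclusion rests on three assumptions: that 24 to 26 applications are planned, that one tube means one application as 9.2 says, and that the Amendment 1 text of 9.5 is current. The pre-amendment text in the same file has the same two sentences. The file also contains the end of a further version whose section 9.5 is not shown.

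**What to change.** Replace the two sentences in 9.5 with one rule, for example: *A subject is compliant if he or she makes 80–120% of the scheduled applications (not of the tubes dispensed), judged from the diary and supplemented by tube weight. Subjects outside this range will be counseled.* Keep tube weight in the rule, since the diary alone does not show how much cream was used.

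If the sponsor wants no upper limit, keep the present definition and change the parenthesis to *less than 80% of scheduled applications*. Either choice removes the contradiction; the sponsor needs to make one.

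In 13.1.1 and 13.1.3, refer to compliance as defined in 9.5.

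The cost is one short paragraph and two cross-references. No new data or procedures are needed, because diary entries and tube weights are already collected. The change should be made before PP membership is determined.
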